RESEARCH PROTOCOL

A RANDOMIZED CONTROLLED TRIAL TO COMPARE HYDROMORPHONE VS FENTANYL IN CHILDREN UNDERGOING TONSILLECTOMY SURGERY

[name]
Clinical Research Coordinator, Anesthesiology
[contact]

[name]
Professor, Otolaryngology
[contact]

[name]
CA3 Resident, Anesthesiology
[contact]

[name], PhD
Assistant Professor, Pediatric Anesthesiology
[contact]

Original Version: January 22, 2020

Revision: February 12, 2020

Revision: March 26, 2020

CONFIDENTIAL: This document is the intellectual property of [name] and [name], PhD. Acceptance of this document constitutes the agreement by the recipient that no unpublished information contained herein will be published or disclosed without prior written approval.

SYNOPSIS

Objective - To compare hydromorphone versus fentanyl for pain control following tonsillectomy or adenotonsillectomy surgery.

Study Period - 2 years

Number of Patients - 300 pediatric patients presenting for tonsillectomy or adenotonsillectomy at St. Louis Children's Hospital (SLCH)

Study Treatment - Hydromorphone vs fentanyl dosed per study design

Study Design - This is a randomized clinical trial with masked assessment, comparing recovery indices for patients receiving intermediate acting versus short acting opioid analgesia using hydromorphone or fentanyl as intraoperative analgesics. An otherwise standardized anesthetic and analgesic regimen will be utilized, consistent with routine care at SLCH. Patients will be randomized 1:1 in blocks of 4 within strata. Patients will be randomized to receive either hydromorphone or fentanyl throughout the perioperative period by opening a sealed protocol envelope.

Inclusion Criteria

1. Children ages 2 to 15 years old
2. Presenting for tonsillectomy or adenotonsillectomy surgery
3. American Society of Anesthesiologists Physical Status (ASAPS) Classification 1, 2 or 3
4. Provide Informed Consent / Assent (as appropriate)

Exclusion Criteria

1. Additional Concurrent surgeries, exclusive of myringotomy tubes, minor oral/nasal procedures (e.g. frenulectomy), and endoscopic procedures
2. Revision tonsillectomy or revision adenotonsillectomy surgery
3. Known pregnancy
4. Any condition which would make the participant, in the opinion of the investigator or the attending anesthesiologist caring for the patient, unsuitable for the study.

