connected to the patient as per standard of care. Patients will be randomized to receive either hydromorphone or fentanyl in the operating room determined by opening a sealed protocol envelope. Administration and dosing of the randomized opioid to each case will be under the direction of the primary anesthesia team under the direction of the pediatric anesthesiologist caring for the child. In addition to the randomized opioid, patients will receive non-opioid analgesics and PONV prophylaxis as per routine care at SLCH. Blinding will be achieved using syringes prepared by SLCH investigational pharmacy.

4.7.4 Optional opioid Plasma Concentration Assessments. Approximately 3 mls of whole blood will be collected from patients at three time points: 1) within 10 minutes of administration of study drug, 2) within 10 minutes of PACU arrival, and 3) within 10 minutes of PACU discharge. Blood samples will be collected through an additional IV line placed in the surgical suite after anesthesia is given. Opioid (hydromorphone or fentanyl) blood levels will be measured using mass spectrometry. This type of analysis does not require *apriori* knowledge of the medication administered and will maintain the masking protocol. A Population Pharmacokinetic Analysis will be performed. The patient may decline to participate in the blood draw component of the study and remain in the study for data collection relating to the primary endpoint. Additionally, failed or missed blood draws in individual patients will not adversely affect the population analysis.

4.8. Treatment Regimen. Patients will receive a general anesthetic as per the standard of care at SLCH. Analgesia will include opioids and non-opioid adjuvants for pain in addition to anti-emetics per routine care at SLCH. Airway maintenance will be via an endotracheal tube supervised by the anesthesiologist responsible for the care of the patient in the operating room.

4.9. Method for Assigning Subjects to Treatment Groups. Patients will be randomized to either hydromorphone or fentanyl in the preoperative area prior to presenting to the operating room by investigational pharmacy staff. Randomization will be 1:1 in blocks of 4 within strata. Stratification will be done by age group (2-7, 8-12, and 13-15), and OSA diagnosed using sleep polysomnography within the last year.

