4.10. Preparation of the Study Drugs. Equi-analgesic dose tables poorly accommodate differences in rapid redistribution between drugs. Establishing a definitive therapeutic equivalence between hydromorphone and fentanyl for the patient population, type of stimulus, and duration of procedure is challenging *a priori*. Previous data gathered at SLCH and clinical expertise guide our dosing choices. Hydromorphone, when utilized as the sole opiate intraoperatively is dosed with median 10 ± 4 mcg/kg with 16 mcg/kg as the 80th percentile, and fentanyl is dosed with median 0.9 ± 0.5 mcg/kg, with 1.5 mcg/kg at the 80th percentile. We will use these current medians to guide our dosing. We will initiate medication dosing of patients with hydromorphone 10 mcg/kg, and fentanyl 1 mcg/kg. Conveniently, formulary preparation of hydromorphone is at 500 mcg / ml and fentanyl at 50 mcg/ml. Thus, blinding should be achievable as the same volume of medication (ml/kg) can be safely administered for each drug.

CONFIDENTIAL: This document is the intellectual property of [name] and [name], PhD. Acceptance of this document constitutes the agreement by the recipient that no unpublished information contained herein will be published or disclosed without prior written approval.

Regarding feasibility, we conducted an informal survey of attending anesthesiologists at SLCH. We had an approximately 50% response rate and all were willing to give these two drugs at the proposed doses in a blinded fashion.

5. Study Procedures

5.1. Screening for Eligibility. The patient's medical record will be screened for: age of child, type of surgical procedure planned, history of previous surgery, classification score for anesthesia, whether child is in custody of a legal caregiver, and ability to consent/assent to the study.

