After transferring from Phase I recovery, a member of the research team will continue to evaluate patient's pain using the same scale on arrival and before discharge. The patient's level of pain (rFLACC) and need for any additional analgesic medications will also be evaluated. rFLACC is standard of care at SLCH and all personnel are well versed in its application. After discharge, the patient will receive a telephone call or text at 24 hours after surgery to evaluate post-operative nausea and vomiting and the level of pain at home. The need for additional pain medication will also be assessed. This is standard of care at SLCH and performed for all patients who are discharged the day of surgery, regardless of type of surgery. Respiratory events will be assessed initially using SpO₂ monitoring immediately after arrival to the PACU, followed by clinical assessment after PACU discharge. Postoperative nausea and vomiting is assessed using observation and patient verbalization.

CONFIDENTIAL: This document is the intellectual property of [name] and [name], PhD. Acceptance of this document constitutes the agreement by the recipient that no unpublished information contained herein will be published or disclosed without prior written approval.

Patient and family satisfaction with care will be assessed using a survey on postoperative day 3, as well as the validated NIH PROMIS questionnaires for Pediatric Self-Report (ages 8-17) and Parent Proxy Report (ages 5-17). We will use the following NIH PROMIS questionnaires: Pain Behavior, Pain Interference, and Pain Quality. PROMIS questionnaires will be sent to patients via e-mail through the REDCap server on postoperative day 7 (\pm 1 day).

5.4. Safety and Compliance Monitoring. All patients will be monitored by an anesthesiologist for the first 5 minutes in the PACU and then every 5 minutes by a registered nurse until discharged from the PACU to the Same Day Surgery unit. Monitoring is continuous until the patient recovers from anesthesia and then every 5 minutes x3, then every 15 minutes until PACU discharge. The same tool, the rFLACC, is used throughout the hospitalization to assess pain. Postoperative nausea and vomiting is assessed using observation and patient verbalization.

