5.5. Medical Monitoring. The PI will be monitoring all unblinded data as it is collected throughout the study and share the information with the anesthesiologists and the surgeons. In general, the Department of Anesthesiology has developed a specific set of Standard Operating Procedures (SOPs) for clinical research. All individuals working on study are required to read and be familiar with and compliant with the SOPs. The SOPs are in part developed from and are compliant with the Institutional Guidelines, including those for a) Interactions with the Washington University Human Subjects Review Committee, b) Informed Consent Development and Implementation, c) Subject Recruitment and Screening, d) Subject Management While on Study, e) Adverse Event Reporting. The potential risks of this study are attributable to the use of opioids in the perioperative period.

As already per routine care at SLCH, there will always be a non-study team attending anesthesiologist available both in the operating room and in the PACU to care for the patient in the event of any potential adverse event. This includes the availability of any resuscitation medications and/or equipment including but not limited to naloxone and emergent airway equipment.

5.6. Data Collection Procedures for Adverse Events. An adverse event would be evident as the study data on pain control, respiratory events, and PONV are collected as per routine standard of care.

5.7. Reporting of Adverse Events. Any adverse event will be reported to the IRB within 7 days as required. Any occurrences of serious adverse events or death will be reported within 24 hours.

6. Statistical Plan

6.1. Sample Size Determination and Sample Size Estimation. Sample size estimations were performed to determine the number of patients required to see a 50% reduction in the patients requiring rescue analgesia between the group receiving fentanyl and the

[figure not shown]
CONFIDENTIAL: This document is the intellectual property of [name] and [name], PhD. Acceptance of this document constitutes the agreement by the recipient that no unpublished information contained herein will be published or disclosed without prior written approval.

group receiving hydromorphone. Each estimation assumed achieving 80% Power, Alpha of 5%, 2 study groups at 1:1 ratio, and 20% attrition (equivalent by study group).

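### Section 5.5 has the PI share unblinded data with the anesthesiologists and surgeons during accrual, which conflicts with the blinded drug administration in 4.7.3 and 4.10 and, with fixed blocks of 4, can make later allocations predictable

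*Combined protocol and SAP*

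**What the plan says.** On monitoring, 5.5 says: "The PI will be monitoring all unblinded data as it is collected throughout the study and share the information with the anesthesiologists and the surgeons". It does not say whether the shared information is pooled or by child, when it is released, or whether the recipients are study investigators or all treating staff.

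On blinding, 4.7.3 says "Blinding will be achieved using syringes prepared by SLCH investigational pharmacy". Section 4.10 adds that "blinding should be achievable as the same volume of medication (ml/kg) can be safely administered for each drug", and reports of the attending anesthesiologists who answered a survey that "all were willing to give these two drugs at the proposed doses in a blinded fashion".

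On who acts and who assesses:
- Section 4.7.3: "Administration and dosing of the randomized opioid to each case will be under the direction of the primary anesthesia team".
- Sections 4.4 and 5.4: the attending anesthesiologist goes with the child to the PACU, and an anesthesiologist monitors the first 5 minutes there.
- Section 5.3: recovery nurses score pain in the PACU. After Phase I, "a member of the research team will continue to evaluate" pain.

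On allocation, 4.9 says "Randomization will be 1:1 in blocks of 4 within strata", and the synopsis gives the same block size. The strata are three age groups and OSA on polysomnography. Section 4.9 has pharmacy staff randomize before the child reaches the operating room. Section 3.1 places randomization in the operating room, and 4.7.3 does so by opening a sealed envelope there.

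**The concern.** The same clinical group is meant to be blind to the drug and is also a named recipient of unblinded data while children are still being enrolled. The primary aim (3.1) is need for rescue opioid. The plan gives no trigger for rescue and does not say who decides on it, so the endpoint is open to judgment.

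Bias can enter in two ways. A child's allocation may be shared before that child's PACU outcome is complete, or known past allocations may let staff predict the next one. By-arm results from past children would not by themselves move rescue between arms while the current child's arm is unknown.

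The effect need not pass through the rescue decision. The anesthesia team directs administration and dosing of the study opioid, so a known or guessed arm could change the amount given and, through it, the need for rescue. Expectations in favor of hydromorphone are on record: the study hypothesis (3.1) and the PACU nurses' impression (1.1, 2.1). Bias of this kind cannot be repaired in the analysis.

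**Working it through.** The plan gives no predictability figure to reproduce. The check compares the passages and then enumerates the stated block design.

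**1. Passages side by side.** Sections 4.7.3 and 4.10 blind the anesthesiologist giving the drug. Section 5.5 sends unblinded data to the anesthesiologists as data accrue. No other passage restricts that sharing. Section 7.1 limits data access to the study team, which sits badly with 5.5. The masked assessment in 4.1 and the masking statement in 4.7.4 are not directly contradicted.

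**2. Predictability.** Inputs: 1:1 allocation in a fixed block of 4 (synopsis, 4.9), so 6 equally likely sequences. Assume all earlier allocations in the stratum are known, and guess the arm with more places left.
- Chance of a correct guess at positions 1 to 4: 1/2, 2/3, 2/3, 1. Mean = (1/2 + 2/3 + 2/3 + 1)/4 = 17/24 = 70.8%.
- Assignment certain: always at position 4, and at position 3 in 1/3 of blocks. (1 + 1/3)/4 = 33.3%, about 100 of 300 children if all blocks fill.

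If each earlier allocation in the block is known only with probability 25%, 50% or 75% (block position still known), 2.1%, 8.3% or 18.8% of assignments are certain, and the best guess is right 55.4%, 59.9% or 64.6% of the time.

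**3. Illustrative effect on the primary comparison.** The size of any shift is an assumption. Other inputs: no true effect, rescue centered on 35% (6.1), 150 per arm (300/2), pooled two-proportion z test at two-sided 5%.
- Let g be the probability of a correct guess, and s the difference in rescue between children guessed to be in one arm and the other. The false arm difference is d = s × [g − (1 − g)] = (2g − 1)s. With g = 17/24, d = 0.417s.
- Rejection probability = Φ[(d − 1.96·SE0)/SE1] + Φ[(−d − 1.96·SE0)/SE1]. Here SE0 = √(2 × 0.35 × 0.65/150) = 0.0551, and SE1 is the unpooled standard error at 0.35 ± d/2.

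| Earlier allocations known | s = 5 points | s = 10 points | s = 20 points |
|---|---|---|---|
| 25% | 5.1% | 5.4% | 6.8% |
| 50% | 5.4% | 6.5% | 11.1% |
| 100% | 6.7% | 11.7% | 32.7% |

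In the 100% row, d is 2.1, 4.2 and 8.3 points. Simulating the stratified blocked design (6 strata of 50, blocks of 4, 40,000 runs) gave 5.1% with no shift, then 6.6%, 11.5% and 31.5% for the 100% row.

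If the current child's arm is known outright and rescue in one arm moves by 2.5, 5 or 10 points (0.35 against 0.325, 0.30 or 0.25), the same test rejects 7.4%, 15.2% or 47.2% of the time.

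**4. Envelope and pharmacy.** The synopsis, 3.1, 4.7.3 and 4.9 do not describe one procedure. No passage says who opens the envelope or what it shows. If the anesthesia team opens an envelope that names the drug, the syringe blinding fails regardless of 5.5. This is a separate and lesser defect.

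**The case against.** The strongest defense is that 5.5 is loose wording. Section 7.1 says data are reported in aggregate and kept within the study team, and 8.1 involves the investigating physicians in monitoring. Read together, these suggest that the anesthesiologists and surgeons in 5.5 are investigators receiving summaries. Arm-level summaries would not support block prediction, and past by-arm results alone would not shift rescue. Recovery nurses, who score PACU pain, are not named as recipients.

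This does not settle the matter. The aggregate line in 7.1 is a general confidentiality statement and does not limit what 5.5 describes, which is all unblinded data as collected. Section 5.5 does not restrict its recipients to investigators, although its next paragraph does distinguish anesthesiologists outside the study team. Even on the investigator-only reading, a research team member scores pain after Phase I, and nothing keeps that person from the unblinded data. If the word unblinded is a slip, the sentence still needs correcting.

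Part of the objection on size stands. Prediction needs allocations by child, with stratum and order, reaching the treating anesthesiologist before the next child in that stratum. The 33.3% and 70.8% are therefore upper bounds, and partial knowledge does much less harm, as the table shows. The 20-point shift exceeds the planned difference (35% to 17.5%, or 17.5 points), and every shift is assumed. Section 4.10 also sets starting doses at equal volume per kg, so discretion over dosing is not unlimited, although 4.7.3 leaves it with the anesthesia team.

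**Conclusion.** The concern holds. Section 5.5 as written is a rule that defeats the blinding in 4.7.3 and 4.10, on a primary outcome with no stated trigger, and it must be corrected. That conclusion rests on the text alone.

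The predictability figures are exact for fixed blocks of 4 but conditional on how much is known: at most 33.3% of assignments certain and 70.8% guessed correctly. The false-positive rates are illustrations. They run from barely above 5%, with partial knowledge and small shifts, to about 33% with full knowledge and a 20-point shift, or 47% with the arm known outright and a 10-point shift. Confidence is medium, because the documents do not show what would be shared in practice or how far behavior would change.

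**What to change.** - **Section 5.5:** state who is masked and until when. Treating anesthesiologists and surgeons, PACU nurses, research team members who score outcomes (5.3), and any PI who treats or assesses trial children should stay masked to individual allocations and by-arm data until database lock. They receive safety data pooled only, with individual unmasking confined to emergencies.
- **Section 4.7.4:** withhold plasma drug results from the same people until lock, because the result identifies the drug.
- **Section 8.1:** route any by-arm safety review to a person who neither treats nor assesses trial children. The independent anesthesiologist could serve, but practices at the same hospital, so the site must confirm that this condition is met.
- **Synopsis, 3.1, 4.7.3, 4.9:** reconcile into one concealed procedure. Pharmacy allocation with masked syringes, as in 4.9, is the version consistent with the stated blinding.
- **Block sizes:** have pharmacy vary them and hold them in a pharmacy-only document. This supports masking and does not replace it. In a simulation with sizes 4, 6 and 8 equally likely and 50 children per stratum (assuming 300 split evenly over 6 strata), certain assignments fell from 33.3% to 2.3%, but best guessing fell only from 70.8% to 67.7% when past allocations were still shared.

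The cost is wording changes, a new pharmacy randomization list and a small change of role in 8.1. The PI loses by-arm access during the trial. Sample size, treatment and visits are unchanged.
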